6.6. Compensation for Research-Related Injury

Does the research involve greater than minimal risk to subjects?

- Yes** **No**

6.7. Economic Burden to Subjects

Does the research involve any costs to subjects?

Yes No

6.8. Vulnerable Populations

Will pregnant women be enrolled?

Yes No

- The procedure in the study is not a part of the standard care at Tufts Medical Center for parturients. However, it is not uncommon for music to be played in the operating room during cesarean delivery, at the patient's request.
- This study's risk to the fetus is NOT greater than Minimal Risk.
- No inducements, monetary or otherwise, will be offered to terminate a pregnancy and that in the case of a fetus; the fetus is not the subject of a planned abortion.
- Research team will have no part in any decisions as to the timing, method, or procedures used to terminate a pregnancy or in determining the viability of a neonate.

Will the research involve neonates of uncertain viability or non-viable neonates?

Yes No

Will subjects who are not yet adults (neonates, children, teenagers) be enrolled?

Yes No

Will minors who are:

- married, widowed, divorced; or
- the parent of a child; or
- a member of any of the armed forces; or
- pregnant or believes herself to be pregnant; or
- living separate and apart from his/her parent or legal guardian, and is managing his/her own financial affairs

be approached for study participation for either themselves or their child?

Yes No

Will wards of the state and/or children at risk of becoming wards of the state be enrolled (this includes foster children or any child that is in state custody)?

Yes No

Will cognitively impaired adults (adults with impaired-decision making capacity) or adults who may lose the capacity to consent be enrolled?

Yes No

Will prisoners be enrolled?

Yes No

Will students and/or employees be enrolled in this research?

Yes No

7. Adverse Event Monitoring

7.1. Definitions

The study does not carry a higher risk of adverse events than typically expected. Also, there is a risk of injury to the tympanic membrane if the music is too loud. The risks to the infant, which will initially be intra-uterine during the study and eventually delivered by the end of the study will be minimal.

Unanticipated problems: any incident, experience, or outcome that meets **all** of the following criteria: unexpected; related or possibly related to participation in the research; and suggests that the research places subjects at a greater risk of harm than was previously known or recognized.

7.2. Reporting Procedures

The co-investigator, [name], will be responsible for contacting the principal investigator to report the occurrence of adverse events. The principal investigator will then complete any necessary safety forms, include the Anesthesia Department's Quality Assurance form. Reportable new information will be reported to the IRB per the Tufts Health Sciences IRB's Reportable New Information policy within 5 business days of an event.

8. Statistical Considerations

8.1. Study Endpoints

- Primary endpoint: measurement of patient satisfaction
- Secondary endpoint: measurement of patient anxiety levels, hemodynamics, and postpartum analgesics requirement.

8.2. Statistical Analysis

- Given that our primary outcome is the satisfaction between two groups, we will use a statistical test to compare proportions (the Chi-squared test).
- Given that our secondary outcomes include mean patient anxiety levels and mean blood pressure, we will use a statistical to compare means (Student's t-test).

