2.4. Alternatives

The alternative is not participating in the study.

3. Objectives

The objective of this study is to determine the effect of music on patient satisfaction and anxiety during cesarean delivery. We will evaluate this objective by studying the following outcomes:

- The primary outcome of this study is patient satisfaction. This outcome will be measured using Morgan's "Maternal Satisfaction Scale for Cesarean Section" (MSSCS) on post-operative day one during the hours of 8am-1pm.
- The secondary outcome will include anxiety at several time points (immediately prior to and after neuraxial technique placement as well as at the end of surgery). This will be evaluated using a simple numeric rating score from 0-10, where 0 is no anxiety and 10 is the greatest anxiety.

We hypothesize that parturients exposed to music during cesarean delivery will have greater overall satisfaction and less anxiety.

4. Enrollment and Withdrawal

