5.1. Study Timelines

- Participation begins at the time of consultation for cesarean delivery on the day of surgery, where the co-investigator [name] will approach the participants and ask them to sign the ICF, and it ends after the post-anesthesia check on postoperative day 1. After recruitment and consent, patients will be randomized using a computer-generated randomization scheme will be used to allocate patients to one of the arms of the study.
- The two arms of the study are as follows:
 - Control group: baseline hemodynamics and anxiety screen; no music
 - Intervention group – Mozart: A study investigator will turn on a playlist of pre-selected Mozart music.
- Given our sample size calculation and that not all women who are approached will consent to the study, we expect recruitment to take 12 months.
- The estimated date for primary analyses will be November 2018
- We estimate that it will take an additional 12 months to complete the study, including statistical analysis and manuscript preparation.

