5.2. Procedures

- Is there a placebo control arm?

Yes No

After reviewing their medical records, the co-investigator, [name], will approach parturients meeting inclusion criteria on the day of admission for scheduled cesarean delivery at Tufts Medical Center. The

PROTOCOL TITLE: A Randomized Controlled Trial of Music vs. No Music During Cesarean Delivery on Patient Satisfaction

VERSION DATE: Oct 16, 2017

research study will be explained and parturients will be given an informed consent form to read. After the parturient read through the informed consent form, think about the risks and benefits, and ask questions, she will be asked to sign the form if she wishes to participate in the study. The informed consent form will then be stored in the principal investigator's locked office. Once a study subject is enrolled, the anesthesia provider, obstetric provider, as well as the nurse will be informed that this parturient is part of the study.

Once the subject is recruited, patient demographic data and baseline vitals signs (including anxiety levels) will be collected. All parturients will receive a standardized spinal technique using 1.6 mL of 0.75% hyperbaric bupivacaine with 15mcg fentanyl and 200mcg morphine, which is the typical standard dose at Tufts Medical Center in nulliparous parturients.

Upon entry into the operating room, parturients who are randomized to music will start to listen to the Mozart piano sonatas during the entire procedure, while those randomized to no music will not listen to any music. After at least 5 minutes of listening to music and immediately after the spinal anesthetic is placed, anxiety levels and vitals signs will be assessed again. At the end of surgery, after coming into the PACU, anxiety and vitals will be assessed. Finally, on postoperative day 1, during the hours of 8AM – 1PM, patient satisfaction will be assessed by administering the MSSCS, which should take about 10 minutes to complete. After that, her participation in the study will end.

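### Section 8.2 compares anxiety and blood pressure by an unadjusted t-test although a pre-music baseline is already collected; ANCOVA on that baseline is a low-cost, conditional gain in precision on secondary outcomes

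*Combined protocol and SAP*

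**What the plan says.** Section 8.2 gives the secondary outcomes one sentence: "our secondary outcomes include mean patient anxiety levels and mean blood pressure, we will use a statistical to compare means", with Student's t-test as the method. It names no covariate and no time point, and no other section adds a baseline-adjusted analysis.

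The measurements are set out in section 5.2:

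- **After recruitment:** "patient demographic data and baseline vitals signs (including anxiety levels) will be collected".
- **Start of music:** "Upon entry into the operating room, parturients who are randomized to music will start to listen". In the order of 5.2 this comes after the baseline, so the baseline is a pre-music measurement.
- **First follow-up:** anxiety and vital signs are assessed again "After at least 5 minutes of listening to music and immediately after the spinal anesthetic is placed".
- **Second follow-up:** "At the end of surgery, after coming into the PACU, anxiety and vitals will be assessed".

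Section 3 (Objectives) lists the anxiety time points differently: "immediately prior to and after neuraxial technique placement as well as at the end of surgery". It does not say whether the first of these is the recruitment baseline or a score taken once music is playing.

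**The concern.** Anxiety and blood pressure are each measured before the intervention and twice after it begins. If a woman's earlier value predicts her later one, a t-test on the later value alone leaves that predictable variation in the error term. With 18 to 22 women this can cost a useful amount of power, and recovering it needs no further data.

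What is at stake is the precision of the anxiety and blood-pressure comparisons, not their validity.

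A related ambiguity bears on the choice of covariate. If the pre-spinal anxiety score in section 3 is the recruitment baseline, a between-arm test of it cannot show an effect of music. If it is taken after music has begun, using it as a baseline would adjust away part of the effect under study.

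**Working it through.** **The plan's own figure.** Section 8.3 sizes only the satisfaction score: 130.3 (SD 10.5) against 113.6 (SD 11.9).

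- Difference: 130.3 − 113.6 = 16.7.
- Pooled SD: √((10.5² + 11.9²)/2) = 11.22, so d = 16.7/11.22 = 1.488.
- The exact two-sided t-test at 0.05 gives 79.0% power with 8 per arm and 84.2% with 9, hence 18 in total. Then 18 × 1.2 = 21.6, rounded up to 22.

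Both stated sizes reproduce. Nothing below changes them, because they concern the primary outcome.

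**Inputs for the secondary outcomes.**

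- From the documents: two-sided alpha 0.05 and totals of 18 and 22 (8.3); two arms (5.1).
- Assumed: 1:1 allocation (9 or 11 per arm), normal data, effects of 1 SD and 0.5 SD, and r = 0, 0.3, 0.5 and 0.7. The documents give no r, SD or target effect for anxiety or blood pressure.

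**t-test on follow-up level.** Noncentral t with 2n − 2 degrees of freedom and noncentrality d/√(2/n).

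- n = 9, d = 1: 1/√(2/9) = 2.121 on 16 df, power 51.3%.
- n = 11, d = 1: 1/√(2/11) = 2.345 on 20 df, power 60.7%.
- n = 9, d = 0.5: 0.5/√(2/9) = 1.061 on 16 df, power 17.0%.

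**ANCOVA on baseline.** One degree of freedom fewer, 2n − 3. The variance of the adjusted difference is (1 − r²)(2/n)(1 + F/(2n − 2)), with power averaged over F ~ F(1, 2n − 2) to allow for chance baseline imbalance. On average, relative to the t-test, the variance is multiplied by (1 − r²)(1 + 1/(N − 4)), where N = 2n. For N = 18 and r = 0.5 this is 0.75 × 15/14 = 0.80. At r = 0, 0.3 and 0.7 it is 1.07, 0.98 and 0.55.

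| Setting | t-test | ANCOVA r = 0 | r = 0.3 | r = 0.5 | r = 0.7 |
|---|---|---|---|---|---|
| 9 per arm, 1 SD | 51% | 49% | 52% | 60% | 77% |
| 11 per arm, 1 SD | 61% | 58% | 62% | 71% | 86% |
| 9 per arm, 0.5 SD | 17% | 16% | 17% | 20% | 27% |

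**Break-even.** For a 1-SD effect, ANCOVA and the t-test have equal power at r of about 0.26 with 9 per arm and 0.23 with 11. The worst loss at 9 per arm is at r = 0: 51.3 − 48.6 = 2.7 points.

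**Check.** Simulation of 200,000 trials at 9 per arm and a 1-SD effect gives 51% for the t-test and 48.5%, 52.1%, 60.3% and 76.5% for ANCOVA, in line with the table.

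**The case against.** The planned test is not an error. Under randomization it holds its 5% level, it concerns secondary outcomes only, and the benefit of replacing it rests on an r that the documents do not give. The baseline is taken around recruitment, while the follow-ups come after spinal placement and after surgery. Nothing in the documents shows that r exceeds 0.26 across those events. With a 0.5-SD effect at 9 per arm, power stays at or below 27% over the range examined, so ANCOVA does not rescue the comparison. All of this stands, and it is why the point is low severity.

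Three stronger readings are tempting and are not supported:

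- **That the t-test has an inflated false-positive rate.** At 9 per arm, 29% of trials would show a chance baseline difference above 0.5 SD. In those trials at r = 0.7 the test's type I error is 12.6%, but in the other 71% it is 1.9%. Overall, 0.29 × 12.6% + 0.71 × 1.9% = 5.0%.
- **That 8.2 leaves the choice between level and change from baseline open.** It speaks of mean anxiety levels and mean blood pressure, whose natural reading is the value at follow-up. No section mentions a change score.
- **That the baseline is missing in the music arm, or was taken after allocation was known.** Section 5.1 mentions a baseline screen only under one arm ("Control group: baseline hemodynamics and anxiety screen; no music"), but 5.2 collects it from every recruited subject. Section 5.1 also says "After recruitment and consent, patients will be randomized", without placing the baseline before or after that step. This is missing detail, not evidence of a flaw.

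**Conclusion.** The point holds as a low-severity improvement in precision. Section 8.2 does not use a baseline that section 5.2 already collects.

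At 9 per arm and a 1-SD effect, ANCOVA changes power by about −3, +1, +9 and +25 points at r = 0, 0.3, 0.5 and 0.7. At 0.5 SD the changes are about −1, 0, +3 and +10 points. These figures rest on 1:1 allocation, normal data and the assumed r and effect sizes. The reading of vital signs as including blood pressure is also an assumption.

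The largest gain needs both a high r and a large effect, so it should not be quoted as the expected gain. Whether r lies above the break-even cannot be shown from the documents.

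**What to change.** In section 8.2, state that anxiety and blood pressure after the spinal and in the PACU are each compared by ANCOVA, with arm as factor and the recruitment (pre-music) baseline of the same measure as covariate. State also that no score taken after music has started may serve as the baseline.

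Reconcile sections 3 and 5.2 on the pre-spinal anxiety score. If it is the recruitment baseline, it is the covariate and is not tested as an outcome. If it is taken with music playing, it is an outcome and 5.2 should list it. While 5.1 or 5.2 is being edited, it would help to say that the baseline is recorded in both arms before the allocation envelope is opened.

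Cost: one or two sentences in 8.2 and short clarifications elsewhere, submitted as an amendment for IRB approval under section 10.4. ANCOVA needs no new subjects or measurements. One extra 0–10 rating would be needed only if an on-music score before the spinal is intended and the post-spinal sentence in 5.2 describes a single assessment. The statistical price is up to about 3 points of power if r is below about 0.26 at 9 per arm (0.23 at 11 per arm).

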8.3. Number of Subjects

- A previous study demonstrated that the total satisfaction score in parturients who get midazolam pre-operatively vs. those who do not is 130.3 ± 10.5 vs. 113.6 ± 11.9 , respectively. Although we do not have similar data for music, we expect that the effect of Mozart music will be similar to that of midazolam because both music and midazolam work as anxiolytics and may play an important role in patient satisfaction. Therefore, we will expect to see a similar difference in patient satisfaction.
- Using G*Power 3.1, we determined that in order to detect a difference between the two groups using a two-tailed T-test with power of 80% and alpha of 0.05, the total number of subjects needed is 18. In order to account for 20% attrition rate, the total number of subjects that would be required to complete study aims is **22**.

VERSION DATE: Oct 16, 2017

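### The 80% power in section 8.3 rests on music having nearly the full midazolam effect, and the chi-squared test in section 8.2 neither matches that calculation nor estimates the score difference

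*Combined protocol and SAP*

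**What the plan says.** Section 8.3 takes satisfaction scores with and without pre-operative midazolam, "130.3 ± 10.5 vs. 113.6 ± 11.9", as its planning values. It is open about the gap: "Although we do not have similar data for music". It bridges the gap by analogy: "we expect that the effect of Mozart music will be similar to that of midazolam because both music and midazolam work as anxiolytics". From this it concludes that "using a two-tailed T-test with power of 80% and alpha of 0.05, the total number of subjects needed is 18", and it raises the total to 22 for 20% attrition. It gives no smallest worthwhile difference and no power at any smaller effect.

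Section 3 makes the MSSCS score on postoperative day 1 the primary outcome. For its analysis section 8.2 says: "Given that our primary outcome is the satisfaction between two groups, we will use a statistical test to compare proportions", and names the chi-squared test. It gives no cut-point that would turn the score into a proportion, and mentions neither an estimate nor a confidence interval for the primary outcome.

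**The concern.** Two things weaken the power claim.

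First, the effect size is borrowed from a sedative drug. A shared anxiolytic action makes a benefit from music plausible, but does not show that it is as large. If music helps by less, the trial is more likely than its stated power suggests to end without significance, and a result that does reach significance will tend to overstate the benefit.

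Second, the written primary analysis is not the one that was sized. A chi-squared test on a dichotomised score discards information and does not say by how many points the arms differ. That difference and its precision are what a reader of a trial of about 20 women would need in order to see what the result leaves open. Both matter because satisfaction is the only primary outcome.

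**Working it through.** **Inputs.** From section 8.3: means 130.3 and 113.6, SDs 10.5 and 11.9, two-sided alpha 0.05, power 80%, t-test, 18 evaluable, 22 enrolled. From section 5.1: "The two arms of the study are as follows", with two listed. Assumed here: 1:1 allocation (no ratio is given, and section 8.5 speaks of three arms), normal scores with a common SD, and that the total satisfaction score in section 8.3 is on the MSSCS scale.

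**Reproducing the plan's figure.**
- Difference = 130.3 − 113.6 = 16.7 points.
- Pooled SD = √[(10.5² + 11.9²)/2] = 11.22, so d = 16.7/11.22 = 1.49.
- Noncentral t, two-sided 5%: power is 79.0% with 8 per arm and 84.2% with 9 per arm. Nine per arm gives 18, as stated.
- Attrition: 18 × 1.2 = 21.6, which gives the stated 22. (18/0.8 = 22.5 would give 23, a trivial difference.)

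**What that size can detect with the t-test.** SE = 11.22 × √(2/n) and expected 95% CI half-width ≈ t(0.975, 2n−2) × SE.
- n = 9: SE = 5.29, t = 2.120, half-width ≈ 11.2 points. Solving for 80% power gives 15.8 points, which is 15.8/16.7 = 95% of the midazolam effect.
- n = 11: SE = 4.79, t = 2.086, half-width ≈ 10.0 points. 80% power at 14.1 points, or 84% of the midazolam effect.

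**Power if music does less than midazolam** (the fractions are assumptions, shown as a range):

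| True difference | Share of 16.7 | Power, 18 completers | Power, 22 completers |
|---|---|---|---|
| 16.7 | 100% | 84% | 91% |
| 12.5 | 75% | 60% | 70% |
| 8.35 | 50% | 32% | 38% |
| 4.2 | 25% | 12% | 13% |

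**Size of significant estimates.** These come from simulated t-tests, taking the mean of the significant results in favour of music. At a true 8.35 points they average about 13.9 with 18 completers (13.9/8.35 = 1.67 times the truth) and 12.9 with 22 (1.54 times). At a true 16.7 points the exaggeration with 18 is only about 1.08 times.

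**The test actually written in section 8.2.** No cut-point is given, so assume a split midway between the planning means: (130.3 + 113.6)/2 = 121.95. The expected proportions above it are 77% and 23% at the full 16.7-point effect. Exact power of the uncorrected chi-squared test is then about 66% with 18 completers and 78% with 22. With the continuity correction it is about 40% and 61%. Under this split the 80% is not secured even if music equals midazolam.

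**The case against.** The strongest defence is that the plan hides nothing. It gives its planning values, concedes that it lacks similar music data, and its arithmetic is right. Section 2.1 also cites earlier music studies and a biochemical rationale for the chosen sonatas. All of that stands. The missing data are data comparable to the midazolam scores, so it would be wrong to say that the protocol has no evidence on music at all. None of it, however, supports an effect of 16.7 points on this score.

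Several stronger readings are tempting, and the documents do not support them:

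- A reader might infer that 80% power requires full equality with midazolam. It survives down to 15.8 points with 18 completers, or 14.1 with 22.
- A reader might take 11.2 points as the smallest observed difference that can be significant. That holds only if the observed SD happens to be 11.22. As the sample SD varies, the threshold at 9 per arm runs from about 7.4 to 15.1 points (central 95%). About 20% of significant pro-music results fall below 11.2 if the truth is 8.35, and about 30% if it is 5.
- A reader might infer that any significant result will look as large as midazolam's. With 18 completers only about 18% of significant estimates reach 16.7 points if the truth is 8.35, and about 9–10% if it is 5.
- A reader might infer that a null result will be reported as no effect. Nothing in the plan says so. It simply contains no rule against it.

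It is also fair to object that the t-test figures describe an analysis section 8.2 does not plan. That stands, and it is why the change to section 8.2 has to come first.

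**Conclusion.** The concern holds in a limited form. The total of 18 is not a calculation error; the weak point is an optimistic effect size with no sensitivity range, combined with a primary test that does not match the sizing. With 18 completers the design has 80% power only for effects of at least about 95% of midazolam's, and about one chance in three of detecting half of it. The written chi-squared test would do worse at the planned effect under a midpoint cut.

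These figures rest on 1:1 allocation, normal scores with SD 11.22 and, for the chi-squared test, a cut-point that the plan does not supply. How far music falls short of midazolam, if it does, is unknown; the smaller effects are illustrations, not predictions. The trial can proceed at its present size, but the primary analysis and the power statement should be corrected before any results are seen.

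**What to change.** No extra patients are needed.

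1. **Section 8.2:** replace the chi-squared test for the primary outcome with the between-arm difference in mean MSSCS score, its 95% CI, and the two-sample t-test used for sizing.
2. **Section 8.3:** add that, under that t-test, 18 completers give 80% power only for a true difference of about 15.8 points or more, and about 32% power if music has half the midazolam effect. This sentence is correct only once step 1 is made.
3. **Section 8.2:** state that a non-significant result will be interpreted from the CI (expected half-width about 10 to 11 points) and not as evidence of no effect.

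The cost is a few sentences and a protocol amendment, which section 10.4 sends to the IRB. The downside is that the stated power looks less favourable and a negative conclusion becomes weaker. The change does not raise power for smaller effects; it makes that limit visible. Ruling out a worthwhile benefit would also need a margin on the MSSCS, which the documents do not give; the three steps do not depend on one.
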